Official Title: Clinical Decision Support for Patient Migraine Management

NCT Number: NCT03706794

IRB Number: 2015-5743

IRB Approval Date: 06/30/2021

Statistical Analysis Plan: 06/30/2021

CDST IRB Protocol – September 2020May 2021

SYNOPSIS

Little is known about who adheres to migraine management strategies, and circumstances that enhance adherence. This knowledge is required to develop patient-level interventions to improve adherence to migraine management strategies. This type of intervention is novel, long overdue, and a major step forward in the clinical care of people with migraine. The proposed project will develop and pilot the first patient level intervention designed to improve adherence to preventive and acute migraine management strategies. We plan to identify people most at risk for non-adherence to migraine management strategies. We will randomly assign the subjects to one of two groups; for one group we will develop an individually tailored clinical decision support tool (CDST) (study group), for the other we will provide general headache education (control group).

PRIMARY OBJECTIVE

The primary objective of this study is to describe and analyze how individual differences and circumstances influence adherence to preventive and acute migraine management strategies. Mobile electronic headache diaries will be used to 1) assess the roles of individual differences and conditions in adherence to preventive and acute migraine management strategies, and 2) develop and pilot a tailored clinical decision support tool (CDST) to improve adherence to preventive and acute migraine management strategies.

PRIMARY OUTCOME VARIABLES

The primary outcome variables will be **adherence to acute and preventive migraine management strategies**. All primary outcome variables will be assessed through an electronic headache diary.

STUDY DURATION

The study will last for approximately 5 years. Phase 1 of the project began in April 2016 under the approved Einstein IRB protocol # 2015-5743. We anticipate completing data collection in 2019, and initial data analysis in 2020.

STUDY DESIGN

This study has three phases:

- 1) The first phase is an **iterative qualitative design** with the purpose of developing and refining the CDST app for use in people with episodic migraine.
- 2) The second phase is a **prospective observational design** with the purpose of evaluating the roles of individual differences and conditions in adherence to preventive and acute migraine management strategies.
- 3) The third phase is a **pilot randomized clinical trial** with the purpose of evaluating the CDST app compared to a Headache Education app to improve adherence to acute and preventive migraine management strategies.

STUDY POPULATION

Phase 1 (A & B):

Participants will be included if they 1) have an International Classification of Headache Disorders – 3 beta diagnosis of migraine, 2) self-report between 6 to 14 headache days per month, 3) are currently prescribed a triptan for acute migraine management, 4) are between the ages of 18 and 65, and 5) self-report at least one problem with adherence to preventive and acute migraine management strategies.

Exclusion criteria are 1) probable or confirmed medication overuse headache, 2) a plan to change, or changing preventive or acute migraine medication during study participation, and 3) are pregnant or are planning to become pregnant during study involvement (as triptans are Category C medications).

Phase 2:

Participants will be included if they 1) have an International Classification of Headache Disorders – 3 beta diagnosis of migraine, 2) self-report and diary-confirmed 6 to 14 headache days per month, 3) are currently using one of the following treatments for acute migraine management: triptans, ditans, gepants, NSAIDs, or acetaminophen, 4) are stable on current preventive and acute treatment regimen for migraine, 5) are between the ages of 18 and 65, 6) read English, 7) have capacity to consent, and 8) complete 80% of diary recordings in the first 30 days of monitoring.

Exclusion criteria are 1) probable or confirmed medication overuse headache, 2) a plan to change, or changing preventive or acute migraine medication during study participation, 3) are pregnant or are planning to become pregnant during study involvement (as triptans are Category C medications), 4) psychiatric illness or cognitive difficulties that would interfere with participation in the study, and 4) participated in Phase 1 of the Clinical Decision Support for Patient Migraine Management protocol.

Phase 3:

Participants will be included if they 1) completed Phase 2 of the study, 2) completed at least 80% of diary recordings throughout Phase 2 of the study, and 3) demonstrated poor (<50%) adherence to at least one acute migraine management strategy and at least one preventive behavioral migraine management strategy during study Phase 2.

Exclusion criteria are 1) probable or confirmed medication overuse headache, 2) a plan to change, or changing preventive or acute migraine medication during study participation, 3) are pregnant or are planning to become pregnant during study involvement, 4) psychiatric illness or cognitive difficulties that would interfere with participation in the study.

NUMBER OF PARTICIPANTS

There will be a total of 394 participants.

NUMBER OF STUDY SITES

[figure not shown]
The study will be conducted at:

[figure not shown]
The [name] (Headache & Adherence) Lab, [name].

The Montefiore Headache Clinic, [name].

STUDY FLOW CHART

Phase 1

1. INTRODUCTION

1.1 Introductory Statement

This document is a protocol for a human research study. This proposal will use mobile electronic headache diaries to 1) assess the roles of individual differences and conditions in adherence to preventive and acute migraine headache management strategies, and 2) develop a tailored Clinical Decision Support Tool to improve adherence to preventive and acute migraine management strategies. The purpose of this protocol is to ensure that this study is to be conducted according to ICH GCP guidelines (CRF 21 Part 312), applicable government regulations and Institutional research policies and procedures

2. BACKGROUND

2.1 Background/Prevalence of Research Topic

Migraine is a chronic, painful condition with episodic attacks of head pain, nausea/vomiting, and sensitivity to light/sound (1). Migraine is common, affecting 1 in 7 Americans annually (2). Migraine is the most disabling neurological disease worldwide (3), and costs the U.S. healthcare system \$4.3 billion annually (4). Patient adherence to migraine treatment recommendations is problematic (5-7) and can lead to increased migraine symptoms, burden, and economic cost (5, 8-10). Some people with migraine use preventive migraine management to reduce migraine frequency, and virtually all people with migraine use acute migraine management to reduce the impact of migraine attacks (11-14). Adherence to preventive migraine management strategies involves consistent use of behavioral strategies (regulating stress, sleep, and diet) (15, 16) and sometimes medication (often beta-blockers or antiepileptics). For acute migraine management, triptans, ditans and gepants are the first-line strategy for moderate-severe migraines, and non-steroidal anti-inflammatories (NSAIDs) or acetaminophen are the first-line strategy for mild-moderate migraines (14, 17-19). Acute migraine medications are most effective if taken early during a migraine episode, when head pain is still mild (11, 20-22). Most acute migraine medication use should be limited to avoid medication overuse headache, a secondary headache caused by regular overuse of acute headache medication (Triptans \geq 10 days/month; NSAIDs and acetaminophen \geq 15 days/month). Thus, adherence to acute migraine management requires in-the-moment decision-making (11, 23). Little is known about who adheres to preventive and acute migraine management strategies (individual differences) and when patients adhere to these strategies (circumstances). Certain individual differences (age, gender, education, psychiatric comorbidity and patient beliefs) have been associated with retrospective reports of adherence and pharmacy refill in isolated studies (5, 8, 24-28). Changes in treatment conditions (time of day, weekly migraine frequency, variations in stress and sleep) may be implicated in adherence to acute migraine management strategies (8), but have not been empirically examined. Understanding individual variability in adherence is the foundation to targeting vulnerable populations with adherence interventions.

3. RATIONALE/SIGNIFICANCE

3.1 PROBLEM STATEMENT

Migraine is a common (29), disabling (30), and costly (31) disorder characterized by episodic, painful symptoms. Preventive treatments can reduce migraine frequency (12, 15, 16, 32, 33), and acute treatments can reduce (or eliminate) symptoms of an ongoing migraine episode (11, 14, 17). Efficacy of these treatments relies on patient adherence. Patient adherence to migraine treatment recommendations is problematic (5-8) and can lead to increased migraine symptoms, burden, and economic cost (5, 8, 9). Development of interventions to improve adherence to migraine management strategies could reduce migraine symptoms and the personal, economic, and societal burden associated with migraine (5, 8, 9). Understanding factors associated with adherence to migraine management strategies is the foundation of improving patient adherence.

3.2 PURPOSE OF STUDY/POTENTIAL IMPACT

A clinical decision support tool (CDST) for people with migraine would build upon commonly used daily headache diaries and offer clinical decision support to the people making clinical decisions in their daily lives: patients. Mobile electronic devices are potentially powerful tools to improve adherence to preventive and acute migraine management strategies. Electronic headache diaries are common in clinical treatment of migraine and have high adherence rates (6). Migraine is most prevalent mid-life (34), when the majority of Americans own a smartphone (35). This study will use mobile electronic headache diaries to 1) assess the roles of individual differences and conditions in adherence to preventive and acute migraine management strategies, and 2) develop a tailored CDST to improve adherence to preventive and acute migraine management strategies.

3.3 POTENTIAL RISKS AND BENEFITS

Study risks are minimal. Participants may feel uncomfortable answering questions about their headaches or changing lifestyle factors associated with migraine. These outweighed by the potential gains both for study participants and for people with migraine broadly.

3.3.1 POTENTIAL BENEFITS

Individual study participants, may experience improved knowledge about their own adherence to migraine management strategies, as well as daily variations in headache symptoms, stress and sleep. Participants may experience improvements in their adherence to migraine management strategies, and potentially experience improvements in their migraine management. Regarding societal benefits, this study will identify patterns of individual differences and circumstances associated with migraine management adherence. This will allow for tailored interventions to improve migraine management adherence in the patients who experience the most difficulty with adherence. This study will also test the feasibility and obtain initial effect sizes for a novel tailored intervention to improve patient adherence to migraine management strategies. If successful, this intervention could improve adherence to migraine management strategies, and potentially improve the effectiveness of migraine treatments.

3.3.1 POTENTIAL RISKS

The randomization process inhibits therapeutic choice of participants. It is possible that taking a headache diary will elicit psychological discomfort as it draws attention to each participant's headache activity and associated disability. It is also possible that participants will experience discomfort when provided with education about how their lifestyle impacts their migraine. Finally, there is a risk that a data breach could reveal private information collected as part of the study.

Protections Against Risk - If participants choose to initiate a new migraine medication during the study, they will be removed from the study, but will be offered both the CDST and Headache Education following their participation in the study. Participants randomized to receive Headache Education will be offered the CDST following their participation in the study. Participants randomized to receive the CDST will be offered Headache Education following their participation in the study. Participants will be given a random study identification number. Participants data will either be collected on paper and stored in a locked lab file cabinet, or through REDCap, a secure online data capture software, through the headache diary application. Data will be de-identified and converted to electronic databases and stored in password-protected files on a password-protected computer in the locked lab. The list linking participant names to identification numbers will be kept on paper in a locked file drawer, and destroyed immediately after the last participant information is entered in a de-identified database, no more than 6 months after the last day of data collection. The research assistant will call participants at least once per month throughout the study to assess for adverse events. The PI will also monitor each participant's recorded headache diaries monthly to assess for adverse events. If either of these procedures identify a potential adverse event, the PI will call the participant to assess the potential adverse event. If the event meets adverse event criteria, the PI will immediately inform the IRB and the NIH. If the adverse event requires medical or professional intervention, the PI will immediately contact the participant's primary clinician at the MHC and develop an intervention plan.

4. STUDY OBJECTIVES

4.1 HYPOTHESIS

Primary: We hypothesize that higher education, income and outcome expectancies, female gender, and lower rates of psychiatric comorbidities, will be associated with improved adherence to preventive and acute migraine management strategies.

Secondary: We hypothesize that the use of the CDST will increase adherence to preventive and acute migraine management strategies compared to Headache Education.

4.2 PRIMARY OBJECTIVE

The primary objective of this study is to describe and analyze how 1) individual differences and 2) circumstances influence adherence to preventive and acute migraine management strategies.

4.3 SECONDARY OBJECTIVEs (if applicable)

The secondary objective of this study is to develop and pilot a tailored clinical decision support tool (CDST) to improve adherence to preventive and acute migraine management strategies.

5. STUDY DESIGN

5.1 GENERAL DESIGN

5.1.1 STUDY DURATION

The study will last for approximately 5 years. Phase 1 of the project began in April 2016 under the approved Einstein IRB protocol # 2015-5743. We anticipate completing data collection in 2019, and initial data analysis in 2020.

4/1/2016 – 2/1/2018	Develop CDST app Pilot test CDST app with up to 24 people with migraine Set up recruitment procedures for remainder of study
2/1/2018-10/1/2019	Recruit and run up to 120 people with migraine for the 3-6 months of the study period
10/1/2019-12/1/2019	Clean data
12/1/2019-4/1/2020	Conduct primary analyses and planned secondary analyses
4/1/2020-12/31/2020	Submit primary analyses and planned secondary analyses for publication

5.2 OUTCOME VARIABLES

5.2.1 PRIMARY OUTCOME VARIABLES

The primary outcome variables will be **adherence to acute and preventive migraine management strategies**. All primary outcome variables will be assessed through an electronic headache diary.

Adherence to Acute Migraine Management Strategies.

- a) **Treat Early:** When participants record headache activity, they will record type, timing, and current pain level for each acute medication dose taken. Treating early is operationalized as taking acute medication while the pain is mild.
- b) **Avoid Overuse:** Avoiding overuse is operationalized as taking fewer than 10 triptans and 15 non-specific pain medications (NSAIDs and acetaminophen) per month.

Adherence to Preventive Migraine Management Strategies:

- a) **Adherence to Preventive Behavioral Strategies:** Each participant will record information related to a single strategy: stress management, sleep management, or consistent eating. Participants will record either 1) whether they used a stress management strategy today (assessed each evening; Yes = adherent, No = non-adherent), or 2) when they got in and rose out of bed (consistent bedtime and rise-time; assessed each morning; Within 1 hour of median = Adherent, outside of 1 hr of median = Non-adherent).

Adherent), or 3) whether they ate at least three times that day (consistent eating, assessed each evening; Yes = Adherent, No = Non-adherent).

b) **Adherence to Preventive Medication:** If a participant is taking a preventive medication, they will record whether they took preventive medication each day. Taking preventive medication = Adherent, Not taking preventive medication = Not-adherent.

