5.3.2 ELIGIBILITY CRITERIA

Eligibility will be determined by a phone screen provided by a research assistant, supervised by the PI.

Inclusion/Exclusion Criteria Phase 1 (A & B):

Participants will be included if they 1) have an International Classification of Headache Disorders – 3 beta diagnosis of migraine, 2) self-report between 6 to 14 headache days per month, 3) are currently prescribed a triptan for acute migraine management, 4) are between the ages of 18 and 65, and 5) self-report at least one problem with adherence to preventive and acute migraine management strategies.

Exclusion criteria are 1) probable or confirmed medication overuse headache, 2) a plan to change, or changing preventive or acute migraine medication during study participation, and 3) are pregnant or are planning to become pregnant during study involvement (as triptans are Category C medications).

Inclusion/Exclusion Criteria Phase 2:

Participants will be included if they 1) have an International Classification of Headache Disorders – 3 beta diagnosis of migraine, 2) self-report and diary-confirmed 6 to 14 headache days per month, 3) are currently using one of the following treatments for acute migraine management: triptans, ditans, gepants, NSAIDs, or acetaminophen, 4) are stable on current preventive and acute treatment regimen for migraine, 5) are between the ages of 18 and 65, 6) reads English, 7) has capacity to consent, and 8) complete 80% of diary recordings in the first 30 days of monitoring.

Exclusion criteria are 1) probable or confirmed medication overuse headache, 2) a plan to change, or changing preventive or acute migraine medication during study participation, 3) are pregnant or are planning to become pregnant during study involvement (as triptans are Category C medications), 4) psychiatric illness or cognitive difficulties that would interfere with participation in the study, and 4) participated in Phase 1 of the Clinical Decision Support for Patient Migraine Management protocol.

Inclusion/Exclusion Criteria Phase 3:

Participants will be included if they 1) completed Phase 2 of the study, 2) completed at least 80% of diary recordings throughout Phase 2 of the study, and 3) demonstrated poor (<50%) adherence to at least one acute migraine management strategy and at least one preventive behavioral migraine management strategy during study Phase 2.

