6. METHODS

6.1 INTERVENTION

Intervention occurs only in Phase 3 of the study. All data collection will occur in REDCap (Research Electronic Data Capture), a secure, HIPAA-compliant electronic data capture system hosted by the Research Informatics Core at Einstein (53). Survey collection will occur in the participant's browser. Daily diary collection will occur using an app (Status/Post) developed for this study to connect participants seamlessly to REDCap using an Apple device. Participants who do not have an Apple device will be provided with a study iPod. Interventions will be delivered through the Status/Post app.

Participants will be randomized to receive either the 1) CDST or 2) Headache Education version of the Status/Post App.

- 1) The Clinical Decision Support Tool (CDST) version of the Status/Post app will include several education modules with companion reminders. Education modules are individualized websites linked to the app that provide a consistent source of information about migraine management. Reminders are just-in-time notifications the participant receives in response to their adherence behaviors throughout the study that briefly remind participants about the education they received in response to their behaviors.

All participants will receive the Medication module, designed to provide information regarding appropriate use of acute and preventive migraine medication. Participants will be assigned to one of three behavioral management education module based on their individual adherence to that behavioral management strategy during the Phase 2 of the study. The three behavioral management education modules are: Stress Management, Sleep Management, and Consistent Eating/Hydration. Each is designed to provide education about why the behavioral strategy is important for migraine management, and provide specific tools to help patients improve their behavioral migraine management adherence.

- 2) The Headache Education version of the Status/Post app will include several education modules available in the app designed to increase general knowledge about migraine, including 1) diagnostic criteria of migraine and other common headaches, 2) pathophysiology of migraine, and 3) common comorbidities of migraine and other headaches.

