6.1.2 METHOD OF ASSIGNMENT/RANDOMIZATION

A research assistant will randomize 60 people (n = 30 per group) to either the CDST Group or Headache Education Control Group, using block randomization with random size blocks using a computerized random number generator. Randomization will be stratified by gender. This research assistant will have no contact with any participant after he or she is randomized.

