Chronic Pain Acceptance Questionnaire (CPAQ). The CPAQ (51) is a 20-item survey designed to assess pain-related acceptance that was developed with patients suffering from chronic pain. Items comprise two subscales (Pain Willingness and Activity Engagement) and are rated on a 7-point Likert scale ranging from “never true” to “always true.” The current study uses the headache version. The CPAQ has demonstrated acceptable internal consistency ($\alpha = 0.78-0.82$) and construct validity in pain and migraine samples (51, 74).

Patient Satisfaction

Client Satisfaction Questionnaire (CSQ). The CSQ (52) is an 9-item survey designed to measure users' general satisfaction with human service programs. The CSQ is commonly used in treatment and program evaluation and has demonstrated excellent internal consistency (52).

Program Evaluation. The Program Evaluation survey is an 8-item, study-specific survey that evaluates the extent to which participants deemed the app to be effective (with response options on a 5-point Likert scale ranging from "not at all effective" to "very effective") and the extent to which participants are likely to recommend the app to a friend with migraine (with response options on a 5-point Likert scale ranging from "not at all likely" to "very likely"). Items were based on the program evaluation survey from a previous clinical trial evaluating preventive medication and behavioral migraine treatments (33).

Daily Diary

Morning. The morning diary will include measures assessing a) **Menstruation**, b) **Headache Symptoms** using ICHD-3b migraine criteria (1), c) **Acute Medication Usage** with items used in other headache medication adherence studies (54), and d) **Sleep Behavior**, using selected items from the Consensus Sleep Diary (75).

[figure not shown]
Afternoon. The afternoon diary will include measures assessing a) **Headache Symptoms** using ICHD-3b migraine criteria (1), and b) **Acute Medication Usage** with items used in other headache medication adherence studies (54).

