Evening. The evening diary will include measures assessing a) **Preventive Medication Usage** with an item used in other headache medication adherence studies (54), b) **Headache Symptoms** using ICHD-3b migraine criteria (1), c) **Acute Medication Usage** with items used in other headache medication adherence studies (54), d) **Eating and Hydration Behavior** using one item asking participants to check off each hour during which they consumed food in the past 24 hours, and one item asking participants how many glasses of liquids they consumed in the past 24 hours, e) **Stress Level and Management** using a 0-10 Visual Analog Scale to rate stress level and a single item assessing stress management, and d) **Migraine Disability** using an abbreviated daily version of the MIDAS (36).

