6.3.5 On Study Visits

All study visits occur either over the phone or via scheduled REDCap data capture sessions, which are either accessed through the participant's email on any device, or through the study app on either the participant's personal Apple device or the study-provided Apple device.

Phase 1A & B

Screening

- Research coordinator will assess inclusion/exclusion criteria
- Approximately 20 minutes in length

App Testing

- Interact with CDST or Headache Education version of app 3 times daily for 7 days (Phase 1A) or 30 days (Phase 1B).
- Each diary entry will take between 1-5 minutes

Focus Group:

- At least one participant per focus group; Focus group led by the PI
- Up to 60 minutes in length
- Questions will focus on: 1) User Interface; 2) Message Content; 3) Message Delivery and Frequency, and 4) Overall Satisfaction

Phase 2 and 3

Screening

- Research assistant will assess inclusion/exclusion criteria with the supervision of the PI
- Approximately 30 minutes in length

Electronic Data Collection:

- App-based
- Phase 2: Month 0-Month 3
- Phase 3: Month 3-Month 6
- See schedule of assessments below

Table 6.1.3. Timing of Measures

Month 0 ~20 min.	Demographics Migraine Symptoms Medications Health literacy (Newest Vital Sign) E-health literacy (eHEALS) Pittsburgh Sleep Quality Index (first 4-items) Berlin Questionnaire
Month 0 Month 3 Month 7 ~40 min.	Migraine Disability Assessment Headache Management Self-Efficacy Acute Medication Self-Efficacy - Headache Study-Specific Self-Efficacy

	Outcome Expectancies Headache Specific Locus of Control Pain Catastrophizing Scale Five Factor Mindfulness Questionnaire Chronic Pain Acceptance Questionnaire
Monthly ~20 min.	Migraine Specific Quality of Life 2.1 PROMIS Interference Perceived Stress Scale PROMIS Anxiety PROMIS Depression PROMIS Sleep Disturbance Daily Stress Inventory
Daily	Morning (~3-5 min.) -Menstruation -Headache Symptoms -Acute Medication Usage -Sleep Behavior Afternoon (~1-2 min.) -Headache symptoms -Acute Medication usage Evening (~3-5 min.) -Preventive Medication Usage -Headache Symptoms -Acute Medication Usage -Eating and Hydration behavior -Stress Level and Management -Migraine Disability
Month 7 ~7 min.	Client Satisfaction Questionnaire Program Evaluation

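### The single-strategy recording rule in 5.2.1 and 6.2.1 conflicts with the diary, the sample-size basis and the CDST module choice, and the Phase 3 behavioural analysis lacks a target strategy defined alike in both arms

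*Combined protocol and SAP*

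**What the plan says.** On recording, section 5.2.1 states "Each participant will record information related to a single strategy: stress management, sleep management, or consistent eating", and section 6.2.1 (Efficacy) repeats it. Both then list the three behaviours as alternatives.

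On the diary, section 6.1.3 describes one instrument for everyone. The morning entry covers sleep "using selected items from the Consensus Sleep Diary". The evening entry has "one item asking participants to check off each hour during which they consumed food in the past 24 hours" and "a single item assessing stress management". The timing table in section 6.3.5 lists "Eating and Hydration behavior -Stress Level and Management" among the evening content. None of these items is limited to a subgroup.

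On Phase 3 entry, section 5.3.2 and the synopsis require adherence below 50% on an acute strategy and on "at least one preventive behavioral migraine management strategy during study Phase 2".

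On the intervention, section 6.1 says under the CDST version: "Participants will be assigned to one of three behavioral management education module based on their individual adherence to that behavioral management strategy". All CDST participants also receive the Medication module. The control version gives general migraine education and names no behavioural target.

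On analysis, section 6.4.1 codes each strategy daily as adhered or not. Section 6.4.3.2 refers back to that and models Group, Time and their interaction in the Phase 3 diary data. It does not say which behavioural strategy each person contributes. Section 6.4.4 plans a baseline comparison of the arms on Phase 2 adherence and has the same gap.

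**The concern.** A primary outcome variable has two recording rules that cannot both be followed. Taken literally, the single-strategy sentence would split the behavioural outcome across three subgroups, and no available section says how a participant's one strategy would be chosen in Phase 2.

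The second issue is what the pilot estimates. Section 3.3.1 says the study should yield initial effect sizes for a tailored intervention. A CDST participant gets one behavioural module out of three. If each strategy is compared in all 60, the contrast for sleep, say, includes CDST participants who were given the stress or eating module. Unless those modules also change sleep behaviour, the estimate is pulled towards no effect. A small estimate could then be read as a weak module when it partly reflects who received it.

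**Working it through.** **1. Which passages conflict with single-strategy recording?**

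| Place | Fits one strategy per person? |
|---|---|
| Evening eating and stress-management items (6.1.3, table in 6.3.5) | No: both are listed for everyone |
| Sample size for n = 100 (6.4.2) | No: the 0.37 for stress management is used for the whole sample |
| CDST module choice (6.1) | Not as a choice: with one strategy recorded, adherence has nothing to choose between |
| Morning sleep items and the stress-level rating (6.1.3) | Weak evidence: 5.2.2 makes daily stress, sleep quality and sleep hours secondary outcomes, so such items would be in every diary anyway |
| Phase 3 entry (5.3.2) | Yes: one recorded strategy below 50% meets the rule |

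The conflict therefore rests on the first three rows.

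**2. What is the Phase 3 behavioural outcome?** Sections 6.4.1 and 6.4.3.2 together point to each strategy in all 60. Only the single-strategy sentence points to one strategy per person. An analysis of the target strategy cannot be run from the available text, because a target is described only for the CDST arm.

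**3. The plan's own figure.** Section 6.4.2 states 80% power for an odds ratio of 1.28 with 30 per arm. The inputs are adherence 0.37, correlation of at most 0.6, two-sided 0.05, and cumulative dropout 0.073, 0.172 and 0.216 at months 1, 2 and 3.

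- Average follow-up, taking months of 30 days: 30 × (0.9635 + 0.8775 + 0.806) = 79.4 days.
- A two-proportion calculation on 30 × (effective days) per arm gives these detectable odds ratios: 1.18 with independent days (79 effective days), 1.39 with AR(1) correlation 0.6 (20.2), and 3.13 with exchangeable correlation 0.6 (79/47.8 = 1.65).

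The stated 1.28 is not reproduced. It lies between the first two cases, and since the correlation structure is not given and 0.6 is an upper bound, this does not show it to be wrong. What follows uses only the stated 80%, taken as an assumption.

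**4. Dilution, as an illustration.** Suppose 30 v 30 has 80% power for the effect on a person's target strategy, so that effect/SE = 1.960 + 0.842 = 2.802. Let p be the share of participants for whom a given strategy is the target. Let f be the fraction of the effect that spills over to non-target strategies. Neither comes from the documents.

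- Fraction of the effect seen when a strategy is analysed in all 60: e = p + (1 − p)f
- Power = Φ(2.802e − 1.960)

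| p | f | e | Power |
|---|---|---|---|
| 0.20 | 0 | 0.20 | 8% |
| 1/3 | 0 | 0.333 | 15% |
| 0.50 | 0 | 0.50 | 29% |
| 0.20 | 0.5 | 0.60 | 39% |
| 1/3 | 0.5 | 0.667 | 46% |
| 0.50 | 0.5 | 0.75 | 56% |
| any | 1 | 1 | 80% |

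For equal thirds with no spill-over: 2.802/3 − 1.960 = −1.026, and Φ(−1.026) = 0.15. A simulation of person-level summaries agreed with the rows for f = 0 and f = 0.5 to within about one percentage point. A pooled comparison of target-strategy adherence keeps the 80% by construction, provided its precision equals that of a single strategy.

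**5. If the single-strategy sentence were followed literally.** With an assumed equal split, a strategy-specific contrast would have 10 per arm. Effect/SE becomes 2.802 × √(1/3) = 1.618, and power is Φ(1.618 − 1.960), about 37%.

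**The case against.** The strongest reply is that the single-strategy sentence is a drafting slip. On that view everyone records all three behaviours, section 6.4.1 already defines the outcome as each strategy, and 6.4.3.2 adopts it. The comparison is randomised and valid, so a target-strategy outcome would be a preference and not a correction. Much of this stands: each strategy in all 60 is the most natural reading, and it should be kept. It does not remove the need to correct a sentence that appears twice in the definition of a primary outcome, nor the averaging over people who did not get the module.

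The power figures are also open to challenge. Shares and spill-over are assumed, the 80% was not reproduced, and section 6.4.2 ties it to adherence to strategies generally. If 1.28 was meant as the average effect over all 60, no power is lost against the plan's figure. In a pilot, power is not the main yardstick either. All of that stands, and the figures show only the direction and possible range.

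The proposed pooled analysis has its own weakness. It merges three differently defined binaries (a yes/no report, bed and rise times within an hour of the median, and eating at least three times) into one odds ratio, and it does not estimate each module separately. That is a reason to report both analyses.

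Finally, the text between sections 5.1.1 and 5.2 and Figures 6.1.4 and 6.3.1 were not available. They might state what is recorded or how a target is set.

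**Conclusion.** The recording contradiction is real and needs correcting. The Phase 3 plan should also add a behavioural outcome matched to what each participant was assigned, or would have been assigned. The size of the dilution cannot be derived from the documents. In the illustration, power runs from 8% to 80% depending on assumed shares and spill-over.

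A reader might infer more, and three inferences are not supported:

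- That Phase 3 entry cannot be decided from one recorded strategy. It can.
- That comparing each strategy in all 60 is biased or breaks randomisation. It is a valid comparison of the arms that answers a diluted question.
- That the stated 80% power is really about 15%. Section 6.4.2 does not say the effect refers to a target strategy, and the 15% rests on equal thirds with no spill-over.

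The scope is the behavioural component of the secondary objective. Treating early, avoiding overuse and preventive medication are unaffected, because every CDST participant receives the Medication module. This is a change that should be made, held with medium confidence because some text and figures could not be seen.

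**What to change.** 1. Confirm what the deployed app records, and correct the single-strategy sentence in 5.2.1 and 6.2.1 to match the diary in 6.1.3 and the table in 6.3.5.
2. If all three behaviours are recorded, fix each Phase 3 entrant's target strategy in both arms from Phase 2 diary data, before randomisation. Use the same written rule that assigns the CDST module, including how ties are broken. If randomisation has already happened, apply that rule to the stored Phase 2 data and document the result before any analysis by arm.
3. In 6.4.3.2, prespecify one pooled 30 v 30 comparison of target-strategy adherence, adjusted for which strategy it is and for Phase 2 adherence to it. Still report each strategy in all 60, and state that the pooled odds ratio combines three different definitions. Use the same target in the baseline comparison in 6.4.4.
4. If the app records only one strategy, state how it is chosen, alike in both arms, and how Phase 3 entry and module choice then work.

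If all three are recorded, the cost is low: a check of the app, one corrected sentence in two places, and a short rule plus an outcome sentence. Section 6.3.1 already has staff reviewing each participant's Phase 2 diary for eligibility before randomisation, so no new data are needed. The cost is higher under item 4, where the account of entry and module choice would also need rewriting.
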